1.5 Flow chart

1.6 Investigation procedure for control and intervention group

Week	Before trial begin	0 T0	6 T1	12 T2
Trial measures for control and intervention group				
Documentation training, doctor	•			
Profile of practices participating in trial	•			
Sociodemographic characteristics of medical assistants	•			
Identification of potentially eligible patients – Pre-randomizations lists	•			
Randomization lists	•			
Patient registration sheet (In- and exclusion criteria, reasons for non-participation of patients; If informed consent available: name, first name, telephone number, MMSW score)	•			
CRF, doctor's documentation				
• Detailed sociodemographics, patient		•		
• Patient's current diagnoses		•	•	•
• Patient's current medication		•	•	•
• Height and weight of patient		•	•	•
• Laboratory results of patient (Serum electrolytes K, Na, Serum creatinine)		•	•	•
• Degree of patient's multimorbidity (CIRS)		•	•	•
• Existing co- and multimorbidity of patient (Charlston Comorbidity Index)		•	•	•
• Hospital stays (duration, reason)		•	•	•
Patient questionnaire:				
• General quality of life of patient (EuroQuoL)		•	•	•
• WHO Disability Assessment Schedule (WHO-DAS II)		•	•	•
• Self reported patient adherence (Medication Adherence Report Scale, MARS)		•	•	•
• Attitude of patients to medicinal therapy (Beliefs about Medicines Questionnaire, BMQ)		•	•	•
• Satisfaction of patients with information provided on patients		•	•	•
• Pain: Verbal rating scale		•	•	•

Week	Before trial begin	0	6	12
Visits		T0	T1	T2
Telephone interview with patient				
• Sociodemographics		•		
• Current patient medication		•	•	•
• Adverse drug reactions (ADRs according to general list of adverse events in German Medicines Law trials)		•	•	•
• Patient's hospital stays		•	•	•
• Infirmity index (Sherbrooke Questionnaire)		•	•	•
• Depressivity (Geriatric Depression Scale, GDS)		•	•	•
• Self reported adherence of patient (Morisky)		•	•	•
Measures for intervention group only				
• Intervention: Training for doctors and medical assistants	•			

2 INTRODUCTION

2.1 Current situation and problem

Care for chronically ill patients is a central challenge for medical care in developed industrial countries. Increasingly problems arise as a result of co- and multimorbidity and associated multimедication – the intake of five or more medicines at the same time – something which is exacerbated by the aging population. Multimедication is associated with substantial risks in the form of adverse drug reactions (ADR) and concomitant hospitalization and increased mortality.

2.2 Background

The risk of inappropriate prescriptions (interactions, non-observance of renal dose adjustments, non-observance of contraindications, inappropriate choice of medicines with regard to age and sex and associated discrepancies in terms of pharmaco-kinetics and -dynamics) rises in line with increasing age, multimorbidity and multimедication.^{1,2,3,4,5,6} Inappropriate prescriptions are determining factors for adverse drug events, especially in the aged.⁷ At the same time the risk of under-prescribing rises in patients on multimедication regimes, and this should be avoided if the therapy is to be optimized..⁸

Multimедication und highly complex medication regimes are associated with poor therapy adherence among patients, whereby modern schools of medicine differentiate between unintended (e.g. technical problems with the intake of medicine, forgetting to take medicine – cognition) and intended non-adherence (e.g. a lack of information about the aim of the prescribed medicine, attitude towards illness and medication, such as a general rejection of pharmacotherapy). Depression is also linked to non-adherence to medical prescriptions.⁹

Discussions between doctor and patient concerning medication are generally initiated by the doctor who tends to control the content to a large degree, focusing on therapeutic benefits and frequently avoiding a discussion of risks, adverse drug reactions and necessary precautionary measures, and rarely checks how much of the content of the interview has been understood by the patient. Patients often fail to inform their doctor when they have changed the dosis of a medicine autonomously, or if they have ceased taking a prescribed medicine.^{10,11}

Evidence from previous studies shows that in order to avoid inappropriate prescriptions

- Regular checks of what medicines have been taken (including OTC medicinal products and dietary supplements – a so-called *brown bag review*) and

The use of *computerized decision support systems*, CDSS, that automatically generate warnings in case of potentially inappropriate prescriptions and present suitable strategies to prevent them.¹²

Communication between doctor and patient is more likely to cover problems concerning medication when patients feel at ease to discuss these in pre-consultation interviews. This effect could also be demonstrated for interventions carried out by medical assistants and was also true for elderly patients. As a result patients showed higher medication and appointment adherence.^{10,13}

2.3 Rationale

Based on the assumptions that

1. Multimorbidity, multimедication and increasing age increase the risk of inappropriate prescriptions and adverse drug events
2. Multimедication and high medication complexity reduce patient adherence.
3. Discussions between doctor and patient on medication-related problems generally focus on the benefit of a therapy and are dominated by the doctor
4. Patients do not usually inform their doctor about changes they make in their medication intake

An intervention was developed that includes the following components:

- (1) Collection of information on the actual medication intake (*brown bag review*) and medication-related problems (technical handling, potential adverse drug reactions, patient preferences) by means of a checklist (MediMoL) in a pre-consultation interview conducted by a medical assistant.
- (2) The use of a medication information system (AiD+)
- (3) Consultations between family doctor and patient on medication-related problems.

Brown bag review and MediMoL provide the family doctor with structured information. This can then be checked by means of the AiD+, that warns the doctor of potentially inappropriate prescriptions, the need for renal dose adjustments and of unintended duplicate prescriptions.

The pre-consultation interview with the medical assistant should enable patients to discuss their problems with the family doctor and to tell him about their expectations, wishes, fears, concerns etc.

The family doctor and patient then discuss necessary changes in the therapy and decide on a new medication. We expect that after taking into consideration the AiD+ warnings and the patient's problems taking the medicine, as well as his or her dislikes and preferences of the patient, the adapted medication will be more suitable, leading to a reduction in potentially inappropriate prescriptions and medication complexity. Furthermore, we expect a prioritization of the medication will take place (as a result of directly asking and taking into account the patient's perspective).

In consequence it is to be expected that patients are more satisfied with the information they have received on their medication and are more likely to adhere to the doctor's instructions. Their health can be improved through the avoidance of undertreatment in pain therapy and possibly through a reduction in adverse drug reactions and associated events. As a result their functional situation and general quality of life should be improved.

2.4 Risk assessment

The risk to the patients of the intervention and collection of data for study purposes is low, as in the case of the intervention group detailed information on a patient's medication will be made available thus ensuring that worse treatment than previous to the trial is not possible. In the control group, the treatment provided by the family doctor will not be changed at all, so

that the trial cannot result in any deterioration in treatment in this case either. The trial centre (Institute for General Practice, Johann Wolfgang Goethe-University, Frankfurt am Main) has no influence on the diagnostic-therapeutic decision-making of the family doctors and their patients. The results of the analysis of the appropriateness of the medication will only be available to the trial HQ after a substantial time lag, so that no timely feedback to the participating doctors will be possible. In addition, it is rather unlikely that results will indicate any real danger to patients, as due to the limited nature of the clinical data being collected, only potential risks to patients can be identified. In the unlikely event of the identification of any clinically relevant potential danger to a patient, the family practice concerned will be immediately informed (within two working days of danger to the patient becoming known), and all necessary measures taken to eliminate the danger.

3 AIMS OF TRIAL

The aims of this pilot trial (PRIMUM *Pilot*) are

- (1) To ascertain the **feasibility of an intervention** for the prioritization and optimization of multimедication in multimorbid, elderly patients in general practice and
- (2) To ascertain the **feasibility of a planned cluster-randomized controlled trial** for the evaluation of the effectiveness of this intervention. Taking into account the recommendations for the preparation of a program for clinical trials of 1999¹⁴ and 2001^{15,16} the pilot trial will focus on the following aspects
 - the practicability of the intervention,
 - the recruitability of practices and patients,
 - the ease with which practices can be randomized,
 - estimated sample size for the controlled trial.

The **practicability of the intervention** will be examined mainly on a qualitative level. The examined quantitative factors will be the time involved and the costs of the intervention including training for family doctors and medical assistants.

For the **feasibility of the planned controlled trial** reasons for the non-participation of both patients and practices and the loss to follow up will be documented, along with the time involved for documentation by the family doctor and medical assistant and for patient interviews by phone. In addition, further potential outcome criteria will be looked at very closely.

3.1 Primary Aim

In preparation for estimating the sample size for the planned clinical trial the criterium appropriateness of the medication will be calculated and evaluated on the basis of the *Medication Appropriateness Index (MAI)*^{17, 18}. Furthermore, problems associated with medications will be encoded using the PiDoc©-classification system¹⁹.

- The MAI consists of 10 items which are rated in line with regulations concerning medicinal products: (1) Indication for a drug, (2) Efficacy for the condition, (3) Suitability of medication (regarding all prescribed medication for a 24 hour period), (4) Accuracy of dosage instructions, (5) Practicability of dosage instructions, (6) Clinically relevant

drug-drug interactions, (7) Non-observance of drug-disease/condition interactions, (8) unnecessary prescription of two or more drugs from the same group, (9) Correctness of the duration of the therapy, (10) Choice of the most favourably priced treatment among drugs of comparable efficacy and safety. The rating will take place on a three point scale whereby “1” represents the best rating (expressed as correct, practicable etc. depending on the question, “3” the worst rating (incorrect, impracticable etc. depending on the question) and “2” a middle rating. As an alternative, it is also possible to respond with “not applicable” or “unknown”.^{17,18} In the trial it is not possible to cover all imaginable types of inappropriateness. It is rather the case that the trial is limited to the most commonly observed combinations in the cross-sectional studies summarized in a manual (deposited in the trial master file). Prospective definitions for the rating values were defined for each criterium. Furthermore an evaluation of criterium 10 relating to the most favourably priced alternative will not take place as a rating does not appear possible due to the new discount contracts between the pharmaceutical industry and the various statutory health insurance companies. Therefore only nine of the original 10 items will be evaluated.

- The PiDoc©-classification system, which is based on German empirical studies and takes account of Strand’s classification²⁰ and the PAS-System²¹ - developed to encode problems associated with medication. Formally it is a “categorization system for standardized observance”²² and is constructed in a hierarchical manner with two classification levels in six main problem groups ((A) Inappropriate choice of medication, **WHERE IS B?** (C) inappropriate intake by patient (incl. compliance), (D) inappropriate dosage, (E) Drug interaction, (F) ADR, (G) Other, which may be patient-, doctor- or communication-linked), relevant intervention suggestions and result codes following a completed intervention¹⁹ As a direct interview with the patient is envisaged, only selected items will be used for the qualitative description of medication problems in the trial (see appendix).

In [name] trial group, an MAI Rating incl. the evaluation of individual PiDoc©-criteria will be carried out independently of the project and blinded for the patient’s group membership (intervention vs. control) in order to improve the reliability of the results.

3.2 Secondary Aims

The following parameters were determined in order to identify further suitable target variables for the clinical trial:

1) Complexity of the medication:

- Total number of prescriptions
- Number of single doses / day
- Complexity of the medication regimen (*Medication Regimen Complexity Index*, MRCI²³)

2) Adherence and associated variables:

- Observed adherence reported as the difference between what medication was taken (*brown bag review*) and what was prescribed (doctor’s files)²⁴

- Reported adherence by the patient (according to Morisky ²⁵, *Medication Adherence Report Scale*, MARS ²⁶)
- Patient's attitude towards medication (*Beliefs about Medicines Questionnaire*, BMQ ²⁷)
- Patient's satisfaction with information on medication

3) *Quality of life and maintenance of functional status*

- General quality of life (EuroQuoL) ²⁸
- Functional status in accordance with WHO Disability Assessment Schedule (WHO-DAS II)

4) *Intensity of pain*

- Verbal Rating Scale (VRS)

5) *Days in hospital, or death (regardless of cause)*

6) *Adverse drug reaction (ADR)*

4 PRIMÄRY AND SECONDARY OUTCOMES OF THE TRIAL

4.1.1 Primary Outcome

The primary target criterion of the PRIMUM pilot trial is the change in the MAI scores, i.e. the difference between the base value (T0) and the value after six weeks (T1).

4.1.2 Secondary outcomes

Secondary outcomes are:

1) *Change in MAI score after 12 weeks*

- Difference between base value (T0) and value after 12 weeks (T2)

2) *Change in complexity of medication after 6 and 12 weeks*

- Total number of prescriptions
- Number of single doses / day
- Medication regimen complexity (Medication Regimen Complexity Index, MRCI)

3) *Change in adherence and associated variables*

- Observed adherence measured as the difference between intake (*brown bag review*) and prescribed medication (physician's records) after 6 to 12 weeks.
 - o Discrepancy score, DS (Sum of all differences in drug, time of intake, frequency and dose) / Sum of all prescriptions, $AS > 0.2 = 1$
 - o Overestimate / underestimate of actual intake by the doctor:
Drug Score (DS, Sum of all drugs taken/sum of all prescriptions), $DS < 0.8$ oder $DS > 1.2 = 1.31$
 - o Dose Score (DoS)
 $DoS = d1(a1) + d2(a2) + d3(a3) + \dots / n$

d = Patient intake (0.1) of prescribed medication

n = Sum of all prescriptions

a = Discrepancy rate (actual intake dd / prescribed dd)

DoS<0.8 or DS>1.2=1.31

o Regimen Score (RS)

RS = d1(b1) + d2(b2) + d3(b3) + ... /n

d = Patient intake (0.1) of prescribed drugs

n = Sum of all prescriptions

b = Discrepancy rate (actual frequency of intake per day / prescribed frequency of intake per day)

RS<0.8 oder DS>1.=1.31

- Change in reported patient adherence (Medication Adherence Report Scale, MARS) *after 6 and 12 weeks*
- Change in the attitude of patients to medicinal therapy (Beliefs about Medicines Questionnaire, BMQ) *after 6 and 12 weeks*
- Change in patient satisfaction with information received on medicines *after 6 and 12 weeks*

4) *Change in quality of life and maintenance of functional status after 6 and 12 weeks*

- Change in general quality of life (EuroQuoL)
- Change in or maintenance of functional status in accordance with WHO Disability Assessment Schedule (WHO-DAS II)

5) *Change in intensity of pain after 6 and 12 weeks*

- Verbal rating scale (VRS)

6) *Days in hospital for whatever reason*

7) *Death for whatever reason*

8) *Adverse drug reaction (ADR)*

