Primary and secondary outcomes:	
A) Practicability of intervention
 
 ▪ Estimation of time / cost of intervention including training for GPs and medical assistants 
B) Feasibility of trial
 
 ▪ Reasons for non-participation of patients ▪ Proportion of patients with loss to follow up compared to entire population ▪ Feasibility of taking measurements T0, T1 (Time required by GP and medical assistant for documentation, content and duration of patient interviews) 
C) Test potential outcome criteria for the main trial:
 
 1. Appropriateness of medication (potential primary outcome criterion in the main trial): the appropriateness will be rated by two experts independently and blinded with regard to the group to which the patient belongs by means of the Medication Appropriateness Index (MAI) and selected scales from the PiDoc®-classification system. The feasibility (quantity of trial data required, time consumed by medication review) will be checked and the effect size of the intervention will be calculated before and after, as well as between groups. 2. Medication complexity: 
 ▪ Sum of prescriptions ▪ Number of single doses / day ▪ Complexity of the medication regimen (Medication Regimen Complexity Index, MRCI) 3. Adherence and other factors 
 ▪ Adherence as observed from discrepancies between intake (patient interviews) and the prescription (doctor's documentation) at T0, T1 and T2. 
 - Discrepancy score, DIS (Sum of all discrepancies in medicine, time of intake, frequency and dose / sum of all prescriptions, DIS >0.2=1 - Overestimate/Underestimate of actual intake by doctor: Drug Score (DS, Sum of all drug intake / sum of all prescriptions) DS<0.8 or DS>1.2=1. - Dose Score (DoS): $DoS = d1(a1) + d2(a2) + d3(a3) + \dots / n$ d = patient's intake (0.1) of prescribed medicines, n = sum of all prescriptions, a = variance (actual dd intake/prescribed dd); DoS<0.8 or DS>1.2=1. - Regimen Score (RS): $RS = d1(b1) + d2(b2) + d3(b3) + \dots / n$ d = patient's intake (0.1) of prescribed medicines, n = sum of all prescriptions, b = variance (actual intake frequency per day / prescribed frequency per day); RS<0.8 or DS>1.2=1. ▪ Self reported adherence of patients (Medication Adherence Report Scale, MARS and adherence according to Morisky) ▪ Attitude of patients to medicinal therapy (Beliefs about Medicines Questionnaire, BMQ)

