8.2 Description of therapy in control arm

For the duration of the trial, the patients in the control group will continue to receive the usual treatment from their GP. As a “recommended standard“, the practices in the control group will receive the simplified version of the current geriatrics guideline, parts I and II, published by the Hessen guideline group.²⁹ Practices and patients in the control group have no access to the Drug Information System AiD+ and do not use the 'MediMoL' checklist. In addition, the description of “usual practice” is the object of qualitative research in the pilot trial.

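### Sections 3.2 and 4.1.2 take patients' actual intake for observed adherence from the brown bag review, an intervention step not scheduled in control practices or at weeks 6 and 12, while the synopsis takes it from patient interviews

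*Protocol*

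**What the plan says.** Protocol section 4.1.2 defines the outcome as "Observed adherence measured as the difference between intake (*brown bag review", set against what the physician's records show as prescribed, at 6 to 12 weeks, and derives four scores from it: Discrepancy, Drug, Dose and Regimen. Section 3.2 names the same source: "Observed adherence reported as the difference between what medication was taken (*brown bag review*) and what was prescribed".

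The synopsis (1.4) defines the same outcome differently: "Adherence as observed from discrepancies between intake (patient interviews) and the prescription (doctor's documentation) at T0, T1 and T2".

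Section 2.3 lists the brown bag review in the first component of the intervention: "Collection of information on the actual medication intake (*brown bag review*) and medication-related problems", obtained by a medical assistant before the consultation. In section 8.1 it is step 4 of the intervention-arm procedure, and the result is stored in AiD+ as Medibox 2. On the control arm, section 8.2 says "Practices and patients in the control group have no access to the Drug Information System AiD" (the AiD+ system), adds that the MediMoL checklist is not used, and otherwise provides for usual care.

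The schedule in section 1.6 places a telephone interview covering current medication at T0, T1 and T2 among the measures for both groups. Sections 9.3.6.1 and 13.1.2 describe its content and timing.

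**The concern.** An outcome that is to be compared between arms needs a measurement made in the same way in both. Sections 3.2 and 4.1.2 name one that belongs to the intervention. An analyst who follows section 4.1.2 to the letter finds no control data and no scheduled follow-up data for any of the four scores.

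The more likely damage is a mixture of sources. Section 9.3.7 has the Mediboxes delivered electronically for analysis, so brown bag data will be on hand for one arm only. If they are used there and interview data are used for controls, the arm difference compares drug packages entered by practice staff with a telephone report to Trial HQ. The pilot is meant to show which further variables suit the main trial, and an unsettled source would weaken that judgement for adherence.

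**Working it through.** The protocol gives no figure to reproduce. The check sets the two candidate sources side by side.

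| | Brown bag review | Telephone interview |
|---|---|---|
| Named as source of intake in | 3.2, 4.1.2 | 1.4 |
| Done by | Medical assistant in the practice (2.3, 8.1) | Trial HQ employee (9.3.6) |
| Arm | Described for the intervention arm only (2.3, 8.1) | Both (1.6) |
| Timing | No visit or week stated; one pass per patient (8.1) | T0, T1, T2 (1.6, 13.1.2) |
| Stored in | AiD+, Medibox 2 (8.1) | Trial database (13.1.2) |

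**Step 1: is the review done in control practices?** Section 8.2 excludes AiD+ and MediMoL by name but does not mention the brown bag review, so its absence has to be inferred. The inference is strong. The both-arm schedule (1.6) does not list it. The investigator training common to both arms (9.1.1) does not cover it. Section 6.1.1 ties the training of the assistant in it to the intervention. Section 10.1 refers to it when patients are asked about acceptance of the intervention. Its data go into a system that controls cannot reach.

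**Step 2: is it repeated at follow-up?** Section 8.1 runs through steps 1 to 9 and ends with the GP closing the intervention. Nothing schedules a repeat at week 6 or 12.

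**Step 3: what follows from a literal reading?** Section 12.3 plans 50 control patients. With no review scheduled for them, 0 of 50 have the intake data that section 4.1.2 names. All four scores use patient intake in the numerator and the number of prescriptions as denominator, so all four are lost for the comparison.

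**Step 4: what would a mixed source do?** Let δ be the true arm difference in a score, and m the mean difference between the score from Medibox 2 and the score from the interview in the same patients. With Medibox 2 in the intervention arm and the interview in the control arm, the expected difference is δ + m. The documents give neither the sign nor the size of m.

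**Step 5: does the interview supply what the scores need?** For long-term drugs, section 9.3.6.1 lists product, dose, prescriber and whether intake has lasted more or less than three weeks.

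- Drug Score needs the drugs taken: listed.
- Dose Score needs actual against prescribed dose: listed, provided the recorded dose is the daily dose.
- Regimen Score needs the daily frequency of intake: not listed.
- Discrepancy Score needs drug, time, frequency and dose: time and frequency not listed.

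The interview guide is in an appendix that is not shown and may hold these items.

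**The case against.** The strongest reply is that the outcome can be measured as planned. The synopsis states a usable definition, the interview is scheduled in both arms at all three visits, and the physician's side of the comparison is on the CRF at the same visits. A reader might infer from section 4.1.2 that adherence cannot be compared between arms at all. The documents do not support that: the data are planned, and the fault is a contradiction about which source counts. This part of the objection stands.

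A second reply is that section 2.2 uses the term generically, for regular checks of what patients take, so that sections 3.2 and 4.1.2 could loosely mean the interview. That is possible, but sections 2.3, 6.1.1, 8.1 and 10.1 use the term for the intervention step, and the text shown contains no rule on which reading governs. The generic use does not remove the conflict.

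A third reply is that no passage actually plans to mix sources. That is correct: section 9.3.7 makes the Medibox data available without assigning them to adherence. Mixing is a risk that the wording leaves open.

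Finally, a reader might suppose that a brown bag review finds more over-the-counter and co-prescribed drugs and so raises the scores in the intervention arm. Section 9.3.6.1 shows that the interview also asks about over-the-counter drugs and the prescriber, and nothing in the protocol supports a direction.

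**Conclusion.** The contradiction is real and should be fixed. Sections 3.2 and 4.1.2 name a source scheduled in neither the control arm nor at weeks 6 and 12; the synopsis names one that is scheduled in both arms at T0, T1 and T2. Read literally, section 4.1.2 leaves four scores without a between-arm comparison. With mixed sources, the comparison carries a method difference of unknown sign and size.

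The conclusion assumes that control practices do no brown bag review, which is inferred from the schedule, the training and the intervention description and is not stated outright. It would go too far to count the review as covering one of the three visits in the intervention arm, because section 8.1 attaches it to no visit.

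The point does not rank as critical. Observed adherence is a secondary outcome, section 12.2 keeps the analysis primarily descriptive, and the MAI outcome, the ICC and the sample size are untouched.

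**What to change.** In sections 3.2 and 4.1.2, replace the brown bag review by the telephone-interview medication list (9.3.6.1), compared with the CRF medication (9.3.4.3), used identically in both arms at T0, T1 and T2 as the synopsis already says. Add a sentence that Medibox 2 data are not used for any between-arm outcome; they may still be described within the intervention arm.

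Before finalising, confirm that the interview guide records time and frequency of intake for long-term drugs, and that the dose recorded is the daily dose. If it does not, add the items, or state that the Discrepancy and Regimen Scores cannot be formed as defined.

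The cost is two wording changes, one added sentence and one check of the guide. No new data collection is needed unless the guide lacks those items.

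### The four observed-adherence outcomes are defined with a 0/1 cut and listed as change outcomes, and the protocol does not say that the underlying ratio is analysed

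*Protocol*

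**What the plan says.** Section 4.1.2 places observed adherence under the heading "Change in adherence and associated variables". It sets out four ratios, each with the number of prescriptions as denominator, and attaches a cut to each.

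- **Discrepancy score:** "Sum of all prescriptions, $AS > 0.2 = 1" in 4.1.2 and "sum of all prescriptions, DIS >0.2=1" in the synopsis (1.4).
- **Drug Score:** "DS<0.8 or DS>1.2=1" in the synopsis.
- **Dose Score:** "DoS<0.8 or DS>1.2=1.31" in 4.1.2.
- **Regimen Score:** "RS<0.8 oder DS>1.=1.31" in 4.1.2.

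The last two are printed differently in the synopsis, which codes values beyond 0.8 and 1.2 as 1. The synopsis band is used below.

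In the same list, the MAI, MRCI, MARS and BMQ appear as changes with no cut. Section 3.2 gives the reason for collecting all these measures: "The following parameters were determined in order to identify further suitable target variables for the clinical trial". Section 12.2 makes the analysis mainly descriptive and leaves procedural detail to the SAP.

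**The concern.** The cut stands inside the outcome definition, and only the observed-adherence measures have one. The natural reading is therefore that the flag is the outcome and its change is what gets compared. A change in a flag registers only crossings of the threshold. Movement that stays on one side of it is not seen, however large, and a small step across it counts in full.

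The pilot uses these measures to judge which outcomes could serve in the main trial. For that it needs to know how far a measure responds, together with its mean, SD and ICC. A flag gives a proportion, and an ICC on a different scale. Judged on the flag, observed adherence could look less responsive than it is. With 10 practices of 5 patients per arm there is little precision to spare.

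**Working it through.** **1. The plan's own figure.** Section 12.3 gives 2 arms x 10 practices x 5 patients = 100, which reproduces. It states no effect size, SD or power for any adherence outcome, so all figures in steps 3 to 5 rest on assumptions.

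**2. What the flag can register.** This step is arithmetic from the stated cut. The flag is 1 if discrepancies / prescriptions > 0.2, and section 6.3.1 requires at least five medicines.

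| Drugs | Discrepancies T0 to T1 | Score | Flag | Recorded change |
|---|---|---|---|---|
| 10 | 6 to 3 | 0.6 to 0.3 | 1 to 1 | 0 |
| 10 | 3 to 2 | 0.3 to 0.2 | 1 to 0 | -1 |
| 8 | 8 to 2 | 1.0 to 0.25 | 1 to 1 | 0 |
| 8 | 1 to 0 | 0.125 to 0 | 0 to 0 | 0 |

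With 5 to 9 drugs the flag needs at least 2 discrepancies, and with 10 to 12 at least 3. A patient at or below 0.2 at T0 cannot improve on the flag. On the three two-sided scores, a move from below 0.8 to above 1.2 also leaves the flag at 1.

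**3. Information lost, normal model.** The relative efficiency of a cut normal score is phi(c)^2 / [p(1-p)], where p is the flagged proportion and c the matching normal quantile.

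| p | Efficiency | 50 per arm is worth about |
|---|---|---|
| 0.5 | 0.64 | 32 |
| 0.3 | 0.58 | 29 |
| 0.2 | 0.49 | 25 |
| 0.1 | 0.34 | 17 |

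For an assumed 0.5 SD effect at 50 per arm without clustering, power is 0.71 for the score and 0.42 to 0.50 for the flag (p from 0.3 to 0.7). With an assumed ICC of 0.1 the design effect is 1 + (5-1) x 0.1 = 1.4, and power is 0.56 against 0.32 to 0.38.

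**4. Power for change in the discrepancy score, simulated.** Assumptions:

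- 10 practices x 5 patients per arm, 5 to 12 drugs each, at most one discrepancy per drug;
- patient discrepancy rate beta-distributed (a+b = 6), T0-T1 latent correlation 0.6, ICC 0.05;
- two-sided 5% t-test on practice means of the T1-T0 change, 1500 runs per scenario.

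| Mean rate | Flagged at T0 | 30% reduction: flag / score (gap) | 40% reduction: flag / score (gap) |
|---|---|---|---|
| 0.15 | 27% | 15.3 / 18.9% (3.6) | 22.1 / 28.1% (6.0) |
| 0.25 | 47-48% | 20.0 / 29.1% (9.1) | 32.5 / 45.5% (13.0) |
| 0.35 | 66% | 24.7 / 45.3% (20.6) | 43.3 / 64.7% (21.4) |
| 0.45 | 79% | 25.3 / 59.0% (33.7) | 50.9 / 82.6% (31.7) |

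Type I error with no effect was 4 to 6%. Adjusting practice means for T0, at a 40% reduction, gives 33.3 / 42.7, 48.6 / 67.4, 58.9 / 86.4 and 64.4 / 96.3%, so the gap remains (9.4 to 31.9 points). Two scenarios in which a drug could count several discrepancies gave 19 against 25% and 23 against 39%, gaps of 6 and 16 points.

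**5. Improvement that the flag misses.** Under the step 4 assumptions, 43 to 58% of intervention patients whose score improved kept the same flag. A second model used Poisson counts with gamma frailty, 5 to 12 drugs and a 30% reduction, without clustering. It gave 52 to 64% at mean scores of 0.1 to 0.4, and 76% at 0.8. The efficiency of change in flag against change in score was 0.33 to 0.61 at mean scores of 0.1 to 0.4, and 0.16 to 0.17 at 0.8.

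**The case against.** The strongest reply is that the protocol never says the flag replaces the score. Section 4.1.2 names the outcomes as scores with full formulae and describes observed adherence as a difference, which is a quantity. The synopsis speaks of levels at T0, T1 and T2. Section 12.2 defers detail to the SAP, which may summarise both. The ratio is computed before it is cut, so no data are lost and mean, SD and ICC can still be obtained. This stands: a reader might infer that the uncut score is discarded, and the document does not support that. It does not remove the point, because what the outcome is belongs in section 4, and section 4 writes a threshold into it.

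Three other stronger readings also fail.

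- **That most movement is invisible.** The documents give no distribution. The share is about half in the main model, and larger in the second model only by assumption.
- **That adherence as a whole would be misjudged.** The MARS is listed as a change without a cut, and Morisky is collected as well.
- **That the power figures hold for all four scores.** Only the discrepancy score was simulated.

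It is also fair to say that power is a secondary yardstick in a descriptive pilot sized for the MAI, and that the simulated tests are not ones the protocol plans. But the same loss of information affects a descriptive judgement of responsiveness. Finally, replacing the two-sided scores by distance from 1 alone would drop the over- or underestimation that the Drug Score is meant to show; the fix allows for this.

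**Conclusion.** The point holds in this limited form: the protocol builds a 0/1 cut into all four observed-adherence outcomes, lists them as change outcomes and does not state that the ratio is analysed. That the flag is coarse follows from the stated cut alone. The size of the loss is conditional on two things: that the flag is used as defined, and the assumed distributions. On those terms, about half of the improvements in the discrepancy score leave the flag unchanged, and power is about 4 to just over 30 points lower at mean rates of 0.15 to 0.45. The loss is small where discrepancies are rare and large where they are common. The point concerns observed adherence as a candidate main-trial outcome. It does not touch the primary MAI comparison or self-reported adherence.

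**What to change.** In sections 1.4 and 4.1.2:

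- Make the uncut score at T1 and T2 the outcome, compared between arms with practice as the cluster and adjusted for the T0 value. Report mean, SD and ICC.
- For the Drug, Dose and Regimen Scores, report the signed score, which shows over- or underestimation, together with its distance from 1.
- Keep the 0.2 and 0.8/1.2 flags as a descriptive proportion, for comparison with the study of elderly patients' drug intake that section 3.2 cites.
- While editing, reconcile the score labels and printed cuts in 4.1.2 with those in 1.4.

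The cost is wording only. The ratio is already computed before it is cut, so no new data or patients are needed. The small downside is that a mean score is less intuitive than a percentage, which is still reported.
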